# **Cover letter**

## **Comparison between the Analgesic Effectiveness of Virtual Reality and Topical Anesthesia: A Clinical Study**

**Date of document: April 28th 2021**

## **Aim**

The aims of the study are to compare the analgesic and anxiety control effectiveness of virtual reality (VR) and topical anesthesia (TA) gel during administration of local anesthesia in adult dental patients, and to determine which approach the patients preferred to reduce pain of dental injections.

The null hypothesis was that there will be no significant difference between the effect of virtual reality compared to that of topical anesthesia gel in reducing pain during administration of local anesthesia injections in adult dental patients.

## **Materials and method**

The study was performed in accordance with the Declaration of Helsinki. Twenty-one adult volunteers visiting the Riyadh Elm University dental hospital participated in the study, with an age range from 22 to 59 years. The procedures were explained to the volunteers in detail and an informed written consent form were signed by each participant. IRB Approval no. RC/IRB/2019/321 was obtained from the Research Center at Riyadh Elm University, Riyadh, Saudi Arabia.

The study was conducted according to the design of split-mouth randomized controlled double-blinded trials. Each participant was randomly allocated to first receive the conventional injection technique under the influence of either *topical anesthesia* or *virtual reality* at the area of the upper second premolar on one side; and then the other procedure on the contralateral tooth after an average of a 10-minute interval. Since it was a split-mouth design, each participant served as his/her own control.

## **Sample Power Calculation**

Sample power was calculated using the G-Power sample power calculator (Universtat Kiel, Kiel, Germany). Given the split mouth study design, an effect size of 0.75 (high effect size) was assumed and for a power of 0.95, the total number of participants was determined as 21.

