## **Statistical Analyses**

The normality of the heart rates observed was calculated and was observed to be within acceptable limits of Kurtosis and Skew. Therefore, parametric tests were used to analyze differences in heart rate. Given the subjective nature of Wong-Baker faces pain-rating scale (W-BFPS), non-parametric tests were used to analyze differences in W-BFPS.

The paired *t* test was used to compare the heart rates of the individuals between the two methods. The Wilcoxon Sign rank test was used to compare the W-BFPS between the two methods. The spearman's correlation was used to check the association between W-BFPS and heart rate for each procedure. All tests were performed at  $p<0.05$ .

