**Table 4 – Differences in Heart Rate according to Gender for each procedure**

	Gender	Mean	Std. Deviation	t*	Sig
Heart Rate Before (VR)	Male	73.4000	6.09554	-2.117	0.048**
	Female	81.6364	10.8284		
Heart Rate After (VR)	Male	73.9000	6.62403	-1.102	0.311
	Female	77.7273	9.92059		
Heart Rate Before (TA)	Male	74.9000	9.65459	-2.118	0.048**
	Female	85.4545	12.7778		
Heart Rate After (TA)	Male	74.1000	7.29459	-.2.369	0.029**
	Female	83.4545	10.3572		

\*\*Differences are significant at  $p<0.05$

A paired t test comparing the change in heart rate per procedure with the gender of the participants, showed no significance for both genders.

The patient's experience of pain with each group was measured using Wong-Baker Faces Pain-rating Scale (W-BFPS). The Wilcoxon Sign Rank test showed that while 10 of the 21 participants had a higher W-BFPS with TA when compared to VR, 5 of the 21 reported a worse experience with VR when compared to TA. There were six individuals who reported the same experience with both procedures (Table 5). These differences were however not significant ( $Z=1.662$ ,  $sig= 0.096$ )

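### The stated power of 0.95 with 21 participants has no sidedness and no definition of the 0.75 effect size; on the simplest reading it is a one-sided figure, and two-sided power is about 0.90

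*Combined protocol and SAP*

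**What the plan says.** Sample Power Calculation names the G-Power program and reports that "for a power of 0.95, the total number of participants was determined as 21". The effect size behind this figure is introduced only by these words: "Given the split mouth study design, an effect size of 0.75 (high effect size) was assumed". The section does not give alpha, the number of tails, the test, the outcome, or the SD that 0.75 is measured against.

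Other sections supply part of this:

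- **Design** (Materials and method): "Since it was a split-mouth design, each participant served as his/her own control". The calculation should therefore be a paired one.
- **Hypothesis** (Aim): the null is that "there will be no significant difference between the effect of virtual reality compared to that of topical anesthesia gel" in reducing injection pain. It has no direction.
- **Tests** (Statistical Analyses): a paired t test "was used to compare the heart rates of the individuals between the two methods", and for pain, "The Wilcoxon Sign rank test was used to compare the W-BFPS between the two methods".
- **Level** (Statistical Analyses): "All tests were performed at" p<0.05, with no mention of one or two sides.
- **Reported p-values** (Results): Table 3 labels its p-values as 2-tailed. The pain comparison is given as Z=1.662, p=0.096, with the comment "These differences were however not significant".

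No section declares a one-sided hypothesis or test.

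**The concern.** A power figure can be checked only if alpha, sidedness, test and effect-size definition are known. Here alpha has to be borrowed from another section and the other three are not tied to the calculation at all. When the calculation is rebuilt in the most natural way, the number 21 appears under a one-sided setting, while the hypothesis and the checkable tests are two-sided.

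If that is how 21 arose, the 0.95 belongs to a test that the study did not run. The type II error at the assumed effect would be about 10% (1 − 0.905) instead of 5% (1 − 0.95). This bears on interpretation because pain, the outcome named in the null hypothesis, was reported as not significantly different, and a reader weighs a non-significant result partly by the stated power.

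**Working it through.** **Inputs.** Effect size 0.75, power 0.95 and n=21 come from Sample Power Calculation. Alpha 0.05 comes from Statistical Analyses. The paired design comes from Materials and method. Sidedness and the meaning of 0.75 are not given, so both are varied below.

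**Formula.** For n pairs and a standardised paired difference d (mean difference divided by the SD of the differences), the paired t statistic follows a noncentral t distribution with n−1 degrees of freedom and noncentrality d√n. Power is the probability that it exceeds the critical value.

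**Step 1: reproduce the plan's figure.** Take d=0.75, one-sided alpha 0.05.

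- n=20: noncentrality 0.75×√20 = 3.35; power 0.944.
- n=21: noncentrality 0.75×√21 = 3.44; power 0.953.

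The smallest n that reaches 0.95 is 21, as stated. Two-sided alpha 0.10 would give the same result, but no section uses that level.

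**Step 2: the same effect, two-sided alpha 0.05.**

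| n | Two-sided power |
|---|---|
| 21 | 0.905 |
| 25 | 0.949 |
| 26 | 0.957 |

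With 21 pairs, two-sided power reaches 0.95 at d = 0.828, about 0.83.

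**Step 3: the other reading of 0.75.** If 0.75 is a difference in units of the single-condition SD (raw SD), equal in both conditions, the standardised paired difference is 0.75/√(2(1−r)), where r is the within-person correlation. Two-sided power at n=21 is then:

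| r (assumed) | Standardised paired difference | Power |
|---|---|---|
| 0 | 0.530 | 0.638 |
| 0.3 | 0.634 | 0.789 |
| 0.5 | 0.750 | 0.905 |
| 0.59 | 0.828 | 0.950 |
| 0.7 | 0.968 | 0.988 |

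For r from about 0.59 to 0.61, n=21 is exactly the smallest two-sided sample for power 0.95. At r=0.61, for example, n=20 gives 0.949 and n=21 gives 0.959. The documents give no planning correlation. The tables allow only before/after heart rate correlations within one procedure to be derived, and those are not correlations between virtual reality and topical anesthesia.

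**Step 4: sidedness of the reported tests.**

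- Table 3, virtual reality: t=2.063 on 20 df gives two-sided p=0.052, as printed.
- Table 3, topical anesthesia: t=1.056 on 20 df gives two-sided p=0.304, as printed.
- Pain: Z=1.662 gives two-sided p=0.0965, against 0.096 printed. Z was itself rounded, so this is agreement.

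The p-values for the heart rate comparison between the two methods and for the Spearman correlations are not printed, so their sidedness cannot be checked.

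**The case against.** The strongest objection is that the documents show incomplete reporting, not an overstated power. The one-sided setting is an inference. Step 3 shows that a two-sided calculation with a raw-SD effect and a correlation near 0.6 reproduces 21 just as exactly. This stands. It limits the conclusion to a conditional one, and it rules out saying that 21 can only be a one-sided result. It does not rescue the text, because that route needs a correlation which is stated nowhere.

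A second objection is that the consequence is small: 0.905 against 0.953, with the sample already fixed. This also stands. Power of about 0.90 is respectable, and nothing here shows the trial to be underpowered.

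A reader might go further and infer that, since 21 matches a one-sided calculation, the pain result should be read one-sided (p=0.048, in favor of virtual reality) and the null rejected. The documents do not support this. They print the two-sided value, call the difference not significant in both the text and the note to Table 5, and state a non-directional null. Halving the heart rate p-value for virtual reality in Table 3 would likewise say nothing about a null hypothesis that concerns pain between the two methods.

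Finally, the paired t figures are only a guide for pain, which is analyzed by the Wilcoxon test. Six of the 21 pairs were tied, and the plan gives no basis for assuming normal differences in the pain score. A specific Wilcoxon power should therefore not be inserted.

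**Conclusion.** The point holds as a conditional one: **wrong as written, conditional on the effect-size definition**.

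- **Certain:** alpha, sidedness, test, outcome and the meaning of 0.75 are missing from the power statement, and sidedness is missing from the significance statement.
- **Likely, not proven:** the 0.95 is a one-sided figure. On the simplest reading (0.75 as the standardised paired difference, alpha 0.05, paired t test), two-sided power with 21 pairs is 0.905, about 5 percentage points below the stated value.
- **What would make 0.95 right for a two-sided test:** a raw-SD effect with a within-person correlation of about 0.59 or more.

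The number 21 is not an arithmetic error, and the point gives no reason to change the sample or to reread any reported result.

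**What to change.** Keep the 21 participants and the two-sided tests.

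1. In Sample Power Calculation, state the alpha, sidedness, test, outcome and definition of 0.75 that were actually used.
2. If 0.75 is the standardised paired difference, restate the power as: *about 0.90 for a two-sided paired t test at alpha 0.05 (0.95 at an effect of about 0.83)*. Add that pain is analyzed by the Wilcoxon test, to which this figure applies only approximately.
3. If 0.75 was a raw-SD difference, state the correlation that was assumed.
4. In Statistical Analyses, add *two-sided* to the sentence that sets p<0.05.

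The cost is one or two sentences in the first section and one word in the second. The only downside is a slightly less favorable stated power if step 2 applies. No reported result changes.

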## **The inclusion criteria**

- Class I of the American Society of Anesthesiologists (ASA) as approved by the ASA House of Delegates on October 15, 2014; aged 18 and above, both genders.
- Participants are in good general health, take no medications, and have no contraindications to the use of local anesthetic.
- The ability to understand oral and written instructions.

### **Protocol for Injection of Local Anesthetic Solution**

The injection was made with 1.8 ml Xylocaine 20mg/ml (DENSPLY Pharmaceutical, USA); (adrenaline: 1:100.000), delivered in cartridges using a 27 - gauge short needle (0.4 x 25 mm, C-K jet) and sterile non-aspirating syringe.

The anesthetic solution was administered into the buccal sulcus of the treated tooth following a standard technique (Handbook of Local Anesthesia, 2013). The syringe was held parallel with the long axis of the tooth while the tissue was pulled out. The needle was inserted in the mucobuccal fold above the apex of the tooth at 45° with buccal cortical plate of the bone and with the gauge facing the bone. A few drops of local anesthetic solution were deposited immediately before the needle entered the tissue. After 2 to 3 seconds, the needle was advanced apically until the bone was reached and the rest of the solution was administered at a slow rate over approximately 1 minute. The needle was then withdrawn gently and slowly.

### **Procedure with Topical Anesthesia Gel (TA)**

For each participant, the pulse rate was recorded prior to the procedure using an FDA approved pulse oximeter (SantaMedical SM-165 Fingertip Pulse Oximeter, China). The injection site was dried and isolated using a cotton roll and a small quantity of the topical anesthesia Iolite 20% benzocaine (Dharma Research , Miami, USA) anesthetic gel was applied using the end of an applicator stick directly at the site of penetration for 15 seconds and then left for 2 minutes to ensure effectiveness (Handbook of Local Anesthesia, 2013). All the time periods were calculated using Clock App timer available on an iPhone device. The injection of anesthetic solution was performed according to the standard technique mentioned above. After the injection, the pulse rate was recorded a second time.

### **Procedure with Virtual Reality (VR)**

For each participant, the pulse rate was recorded prior to the procedure using an FDA approved pulse oximeter (SantaMedical SM-165 Fingertip Pulse Oximeter, China). The virtual reality standalone headset used in the study was the 128 GB Oculus Quest® (Facebook Inc. USA). The device was loaded with the animated short movie ‘Henry’ (Oculus Story Studio, USA) and then properly adjusted around the patient’s head and in front of her/his eyes. The volume level was controlled and interpupillary distance (IPD) was adjusted by each participant after providing brief instructions. The movie was played for some time prior to administration of the injection to enable the participant to interact and get involved with the scene. The next step comprised of guiding the patients to turn their heads and adapt with the dentist’s instructions while watching the movie. The injection of anesthetic solution was performed according to the standard technique mentioned above while the participants continued watching the VR movie. After the injection, the pulse rate was recorded a second time.

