**Table 3: Significance of difference in heart rate before and after giving the injection for each type of procedure**

		Paired Differences					t*	Sig. (2-tailed )		
		Mean	Std. Deviation	Std. Error Mean	95% Confidence Interval of the Difference					
					Lower	Upper				
With VR	Heart Rate Before - Heart Rate After	1.80952	4.02019	.87728	-.02044	3.63949	2.063	.052		
With TA	Heart Rate Before - Heart Rate After	1.42857	6.20138	1.35325	-1.39426	4.25141	1.056	.304		

\* Calculated using the paired t test Differences are not statistically significant

The patients recorded lower heart rates while in VR than in Topical anesthetic as mentioned earlier. This was true both before and after the dental injections. However, the paired *t* test found the differences to be statistically insignificant both before and after dental injections. While when gender differences were observed it was seen that the females had a higher heart rate compared to the males in each of the four situations. It was observed that these differences were statistically significant for TA-before, VR-before and VR-after (Table 4).

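### The aim is anxiety control during the injection, but no anxiety outcome is named and pulse is read only before the procedure and at an unstated time after the injection

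*Combined protocol and SAP*

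**What the plan says.** The Aim is to "compare the analgesic and anxiety control effectiveness of virtual reality (VR) and topical anesthesia (TA) gel during administration of local anesthesia". Anxiety is not mentioned as an outcome again.

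Both procedure sections schedule two pulse readings. The first: "For each participant, the pulse rate was recorded prior to the procedure using an FDA approved pulse oximeter". In the VR section this sentence stands ahead of loading the film, fitting the headset and adjusting it. The second: "After the injection, the pulse rate was recorded a second time". Neither section gives the delay between needle withdrawal and that reading.

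In the injection protocol, once the needle has reached bone, "the rest of the solution was administered at a slow rate over approximately 1 minute". No pulse reading is scheduled at needle entry or in that minute. With TA the gel is applied "for 15 seconds and then left for 2 minutes to ensure effectiveness"; with VR the lead-in time before the injection is not specified.

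Patient Input adds a pain rating and a preference question, and no anxiety scale. Statistical Analyses plans a paired t test of heart rates between methods, without saying whether levels or changes are compared.

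The Results text after Table 3 states: "The patients recorded lower heart rates while in VR than in Topical anesthetic as mentioned earlier". It adds that this held both before and after the injections, and that neither difference was significant.

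**The concern.** The stated question is about a short event. The readings stand on either side of it, the second at an unknown distance. If pulse rises at needle entry and settles quickly, a before-after comparison can miss the rise; if it does not rise, the same comparison looks the same. A null heart-rate result then neither supports nor refutes anxiety control during the injection. The planned Spearman correlation has a related weakness: it relates a rating of the pain experienced to a pulse that was not taken while the injection was being given.

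The Results wording adds a second problem. It presents the lower heart rates as recorded in VR at both readings, whereas the procedure section places the first one ahead of the headset. A reader could credit VR with a gap that mostly preceded its use.

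**Working it through.** **1. Reproduce the reported tests.** Inputs are from Table 3, n = 21, 20 degrees of freedom, t = mean / (SD/√21), interval = mean ± 2.086 × SE.

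- VR: SE = 4.02019/√21 = 0.877; t = 1.80952/0.877 = 2.063; p = 0.052; 95% CI −0.02 to 3.64.
- TA: SE = 6.20138/√21 = 1.353; t = 1.42857/1.353 = 1.056; p = 0.304; 95% CI −1.39 to 4.25.

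Both agree with the table. The differences are before minus after, so positive values are falls. Neither procedure shows a mean rise across the injection.

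**2. Locate the gap between methods.** Means are from Table 2, in beats/min.

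| | TA | VR | TA − VR |
|---|---|---|---|
| Before | 80.4286 | 77.7143 | 2.71 |
| After | 79.0000 | 75.9048 | 3.10 |
| Fall | 1.43 | 1.81 | |

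Difference in change = 1.80952 − 1.42857 = 0.38, which is also 3.10 − 2.71 to within rounding. The share of the post-injection gap already present at the first reading is 2.71/3.10 = about 88%.

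**3. Precision of the difference in change.** The Results give change within each procedure and levels between methods, but no overall between-method test of change. Its standard error needs the within-person correlation r of the two changes, which is not reported. Assuming r from −0.5 to 0.8:

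SD = √(4.02019² + 6.20138² − 2r × 4.02019 × 6.20138), SE = SD/√21.

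- r = −0.5: SD 8.92; 95% CI −3.7 to 4.4; p = 0.85.
- r = 0: SD 7.39; 95% CI −3.0 to 3.7; p = 0.82.
- r = 0.8: SD 3.84; 95% CI −1.4 to 2.1; p = 0.65.

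No value in this range points to a difference in pre-to-post change. That still says nothing about the minute in between.

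**4. Compare the time windows.** With TA the first reading comes at least 15 s + 2 min = 2 min 15 s before the injection. With VR the corresponding interval is unspecified. The delay to the second reading is unspecified in both. The before-after windows may therefore differ between methods, and the documents do not allow a check.

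**5. Set the text side by side.** If the VR first reading was taken before the headset was fitted, as the order of the procedure section indicates, the phrase *while in VR* is wrong for that reading. If it was taken with the headset on, the statement that it preceded the procedure is wrong and the value is not a baseline. The two places must be reconciled either way.

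**The case against.** The strongest reply has four parts, and much of it stands.

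- **Heart rate is never called the anxiety outcome.** The Results give the purpose of the before-after comparison as the impact of the procedure on heart rate. This is correct. That pulse serves the anxiety aim is an inference, made because nothing else recorded could. The missing definition is part of the point.
- **The second reading may have been immediate.** A reader might infer that the injection response was missed, or put a figure on how much of it had faded. The documents support neither. The delay is unstated, no rate of decay is given, and an immediate reading could retain most of a rise. Small, non-significant mean falls fit a missed rise, no rise, or a raised anticipatory baseline.
- **The wording may be loose shorthand for the VR procedure.** The same paragraph calls the differences non-significant, so no VR effect on heart rate is claimed as shown. That lowers the stakes but leaves the mismatch with the procedure section. A reader might also infer that the 2.71 beats/min gap at the first reading cannot be a VR effect. That is too strong: the headset state is not stated outright, and with an average interval of 10 minutes some carryover in participants given VR first is conceivable.
- **The consequence is limited.** The null hypothesis concerns pain, the pain and preference outcomes are unaffected, and the Results draw no explicit anxiety conclusion. All true. The anxiety aim is still stated, and a reader will look to the heart-rate tables for its answer.

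**Conclusion.** The point holds in a limited form. The aim includes anxiety control during administration; no outcome is named for it, and the only candidate was not sampled during administration. The data show no mean rise (falls of 1.81 with VR and 1.43 with TA) and a difference in change of 0.38 beats/min. Under the assumed correlations the confidence interval for that difference runs from (−3.7, 4.4) at its widest to (−1.4, 2.1) at its narrowest. These figures describe pre-to-post change and cannot settle the anxiety aim in either direction. Separately, the Results wording conflicts with the order of events in the VR procedure, and about 88% of the post-injection gap was already present at the first reading.

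This rests on two inferences: that pulse is meant to serve the anxiety aim, and that the order of sentences in the VR section is the order of events. The first is the only candidate the documents offer; the second is the natural reading.

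**What to change.** **For the data already collected:**

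- Report heart rate as pre-to-post change, compared between methods with a paired test and a confidence interval. The individual readings already allow this.
- Replace *while in VR* with wording such as *in the VR procedure*. State when each reading was taken relative to the headset, the gel and needle withdrawal, or say that this was not recorded.
- State that anxiety during administration was not measured.

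The cost is one short analysis and some rewording, and the heart-rate findings will no longer be read as an answer to the anxiety aim.

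**If the protocol is run again:**

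- Name the anxiety outcome and its time point.
- Leave the same oximeter on and note pulse at needle entry and once mid-deposit in both procedures, and fix the delay to the post-injection reading.
- Make the needle-entry reading the main one, because mid-deposit pulse may also reflect the adrenaline in the solution.

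The cost is two extra readings per injection. Watching a film may itself move pulse apart from anxiety, so a short anxiety scale alongside would help interpretation.
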